6.5.4 Retrieval

Note: The use of a Mechanical Pump for aspiration is not allowed per protocol.

- Optimum control of the Device and microcatheter relative positions during retrieval may be achieved by advancing a torque device over the Device shaft and tightening it against the microcatheter RHV.
- If using a Balloon Guide Catheter inflate the balloon to occlude the vessel as per the Balloon Guide Catheter IFU.
- Withdraw the Device and Microcatheter slowly and carefully as a unit to the Guide Catheter tip while aspirating through the Guide Catheter with a syringe.
- As the device reaches the Guide Catheter, apply vigorous aspiration (by syringe), withdraw the Device and microcatheter into the Guide Catheter and continue to aspirate until the Device reaches the proximal RHV.

Note: If withdrawal into the Guide Catheter is difficult (as may be the case with a large clot burden) then deflate the balloon (if applicable) and withdraw the guide, Microcatheter and Device together through the Introducer Sheath.

- Disconnect the RHV from the Guide Catheter and remove the Device, Microcatheter and RHV together from the Guide Catheter.
- Use the syringe to further aspirate the Guide Catheter to ensure it is clear of any thrombus material.

6.5.5 Cleaning and Re-use

- Each EmboTrap Revascularization Device may be used for up to three (3) retrieval attempts.
- If an additional pass is to be made with the Device then carefully remove any captured thrombus from the Device and clean the Device in heparinized saline, rubbing gently from proximal to distal to remove any residual thrombus material. Inspect the Device carefully and if any damage or deformity is observed do not use the Device – instead use a new EmboTrap Revascularization Device for any subsequent passes. If using the same Device, replace the Insertion Tool onto the proximal shaft and retract the Device into the Insertion Tool until it is fully resheathed.

Do not attempt more than three (3) retrieval attempts in the same vessel.

6.5.6 24 Hour (-8/+12 hrs) Follow-up

The 24(-8/+12) hour follow-up visit includes:

- An NIHSS examination
- CT or MRI imaging.
- Record any adverse events which occur after the procedure and up to the time of the 24 hour examination.

6.5.7 72Hour (± 12 hrs) Follow-up of angiographic screening failures

For patients who were consented but not included due to failure to meet angiographic inclusion or exclusion criteria; record any adverse events which occur up to the time of the 72 (± 12) hour examination.

6.5.8 7 Day/ 168 Hour (± 12 hrs) Follow-up

The 7 Day/ 168 Hour (± 12 hrs) follow-up visit includes:

- An NIHSS examination
- Physical Examination
- Concomitant medications
- Record any adverse events which occur after the 72 hour time point and up to the time of the 168 hour examination.

6.5.9 90 Day (± 14 Days) Follow-up

The 90 Day (± 14 Days) follow-up visit includes:

- An NIHSS examination and an mRS
- Record any adverse events which occur after the 168 hour time point and up to the time of the 90 day examination.

Subjects who successfully complete the 90 day visit will be discharged from the study.

Table 1: Study visits and assessments

Study Requirement	Screening	Procedure	Post Procedure			
			24 Hours (-8/+12 hrs)	72 Hours (± 12 hrs)	7 Day 168 Hours (± 12 hrs) or at Discharge	90 Days (± 14 days)
	Within 8 hrs. of onset of stroke	Time Ø				
Informed consent	X(1)					
Pregnancy test	X(2)					
NIHSS Score	X(5)		X		X(3)	X
Modified Rankin Scale (mRS)	X					X
Medical history	X					
Physical examination	X				X(3)	
Blood Pressure and Pulse	X					
Assess/confirm study eligibility	X					
CT or MRI	X		X			
Angiography	X(6)	X(7)				
Hemoglobin and Platelet Count	X					
Serum Glucose	X					
Serum Creatinine or GFR	X					
International normalized ratio (INR), activated partial thromboplastin time (APTT)	X					
Mechanical thrombectomy procedure (EmboTrap as well as any rescue devices)		X				
Concomitant medications	X				X(3)	
Record adverse events	X(4)	X	X	X(8)	X(3)	X

- (1) Patient or Legally Authorized Representative must sign informed consent prior to screening specific tests which are beyond the local standard of care.
- (2) For females of childbearing potential, subjects must have a documented negative pregnancy test prior to device insertion except in the case of local regulations and ethic committee approvals requiring consent post the emergency situation.
- (3) To be performed at 168 Hours (+/- 12 hrs) or at discharge (whichever occurs first).
- (4) Record all adverse events from the time of signature of the ICF.
- (5) Perform prior to angiography.
- (6) Perform just prior to mechanical thrombectomy in order to verify the angiographic inclusion/exclusion criteria are met.
- (7) Perform angiography after every EmboTrap device pass, at the final EmboTrap device use, after each rescue therapy device pass. Obtain a final angiogram at the end of the interventional procedure.
- (8) Follow up at 72 hours is exclusively for adverse events in the consented but not included patients where they were not enrolled because they did not meet the angiographic inclusion or exclusion criteria.

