12.3 Event notification

12.3.1 Adverse Events (AE) and Adverse Device Effects (ADE)

All adverse events and adverse device effects shall be recorded on sponsor-provided adverse event electronic case report forms eCRF. The safety assessments will consist of Adverse Events (AE) from the time the ICF is signed through Day 90 for those patients enrolled, and to discharge or 72 hours for those patients identified as screening failures through angiographic criteria. Adverse events and adverse device effects shall be recorded in the form of a diagnosis, rather than providing the various signs and symptoms for a particular health condition. The investigator or investigator-appointed study personnel will complete these eCRFs. Adverse event eCRFs should be provided to an appointed Neuravi representative (study monitor) for review within 30 days of becoming aware of the event, and within 24 hours of knowledge of device related adverse events. Copies of related records and reports shall be provided to Neuravi upon request. If the Investigator is made aware of any SAEs after Day 90, these should also be reported to Neuravi or its designee provided the SAE is considered related to the investigational device. The site would then provide a completed SAE form within 1 business day and the event will be followed until resolution, or until adequate stabilization is met.

An AE that occurs after the ICF has been signed and before the treatment with the EmboTrap has started is identified as a pretreatment AE (PTAE). This will include AEs occurring in those patients identified as screening failures through the angiographic inclusion or exclusion criteria. An AE that occurs after treatment using EmboTrap has started will be considered a treatment emergent AE (TEAE). All AEs must be recorded and reported accordingly, whether they appear causally related to the interventional procedure, or not. Adverse events will be followed until the outcome is known or until the Investigator feels no further medical follow-up is warranted.

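### The visit-level adverse-event look-backs in Protocol 6.5.6 to 6.5.9 do not join up for treated patients and contradict the continuous collection required by Protocol 12.3.1 and SAP 14.1

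*Protocol*

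**What the plan says.** Each follow-up visit in Protocol section 6.5 has its own adverse-event look-back:

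- 6.5.6, 24-hour visit (allowed at 16 to 36 h): "Record any adverse events which occur after the procedure and up to the time of the 24 hour examination".
- 6.5.7 and Table 1 footnote 8, 72-hour contact: "Follow up at 72 hours is exclusively for adverse events in the consented but not included patients", meaning those who failed the angiographic criteria.
- 6.5.8, 7-day visit: "Record any adverse events which occur after the 72 hour time point and up to the time of the 168 hour examination".
- Table 1 footnote 3, timing of the 7-day assessments: "To be performed at 168 Hours (+/- 12 hrs) or at discharge (whichever occurs first".
- 6.5.9, 90-day visit: "Record any adverse events which occur after the 168 hour time point and up to the time of the 90 day examination".

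The safety section sets a different rule. Protocol 12.3.1 has adverse events assessed "from the time the ICF is signed through Day 90 for those patients enrolled" and adds: "All AEs must be recorded and reported accordingly, whether they appear causally related to the interventional procedure, or not". Table 1 footnote 4, attached to the screening cell, reads "Record all adverse events from the time of signature of the ICF". SAP 14.1 likewise expects events during or after the procedure, up to the 90-day follow-up, to be in the database.

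**The concern.** A coordinator working through the visit schedule for a treated patient stops at the 24-hour examination and resumes at 72 h. The 72-hour point that opens the 7-day look-back is a contact treated patients do not have. Screen failures, who never received the device, are asked about events up to 72 h; treated patients are not. A similar question arises later. The 7-day assessment moves forward to discharge, but the 90-day look-back is still anchored at 168 h.

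The early post-procedure days matter for the adverse-event tables and for the count of procedure-related serious events (PRSAE), which SAP Table 1 takes per patient without a time limit. The safety results of this open-label, single-arm trial are descriptive (SAP 13.2). There is no comparator arm in which the same omission would occur, so any omitted event can only lower the reported rate. The Clinical Events Committee can adjudicate relatedness only for events that reach it.

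**Working it through.** The plan states no figure on this point, so there is none to reproduce. The check is subtraction between the stated windows, then a comparison with the safety section.

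**First interval: 24-hour examination to 72 h, treated patients**

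Inputs: examination time e, nominally 24 h and allowed from 16 to 36 h (6.5.6); start of the 7-day look-back s = 72 h (6.5.8).

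Unprompted time = s − e:
- e = 24: 72 − 24 = 48 h, which is 48/168 = 28.6% of the first week
- e = 16: 72 − 16 = 56 h
- e = 36: 72 − 36 = 36 h

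If the ±12 h tolerance of the screen-failure contact were borrowed for s (60 to 84 h), the range would widen to 60 − 36 = 24 h and 84 − 16 = 68 h. Treated patients have no such contact, so the nominal 72 h is the natural value.

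**Second interval: early discharge visit to 168 h**

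This depends on what the 168-hour point in 6.5.9 means.

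- Clock time: unprompted time = 168 − d for a discharge visit at d hours. The documents give no discharge times. For assumed values, d = 72 gives 96 h, d = 96 gives 72 h, d = 120 gives 48 h and d = 144 gives 24 h.
- The 7-day/discharge visit itself: the look-backs join and the interval is 0 h.

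For clock time: the parallel phrase in 6.5.8 can only be clock time for treated patients, who have no 72-hour visit. For the visit reading: Table 1 puts 7 days, 168 h and discharge in one column as a single visit. The text does not settle it.

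**Comparison with the safety section**

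Under 12.3.1 collection runs from consent to Day 90, so uncovered time is 0 h for both intervals. The two sets of instructions disagree, and I found no clause saying which prevails.

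**What could be affected**

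- Deaths: reported within 24 hours of awareness (5.3). Procedure-related mortality at day 7 is the least exposed.
- SAEs and SADEs: notified within 24 hours of awareness, whatever the visit (12.3.2). The exposure is limited to events the site does not learn of without asking. A procedure-related one would be missing from the PRSAE count.
- Non-serious adverse events: no comparable immediate route in general, so the visit prompt matters most here.
- Events reportable even without sequelae, such as asymptomatic intracranial hemorrhage (section 12): these need not be SAEs, so 12.3.2 need not catch them.

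**The case against.** The best reply is that the plan already requires continuous collection. Section 12.3.1 and SAP 14.1 leave no period out. The named safety endpoints are serious events or deaths and come in through event-driven notification rather than visit look-backs. SAP Table 1 also measures the secondary SADE endpoint over 24 hours post-treatment, so on that definition an event between 24 and 72 h does not enter it. Completed eCRFs are 100% verified against source (15.1), and an extra NIHSS is required at any sign of deterioration (7.2).

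Much of this stands, and it rules out two stronger readings. A reader might infer that treated patients have no adverse-event collection in these intervals, so that SADE, PRSAE and day-7 mortality are under-collected. The documents do not support that: they require the collection and give serious events and deaths a separate route. A reader might also reckon that a patient discharged before 72 h loses 168 − 24 = 144 h, or 86% of the first week. That needs an assumed discharge time, the clock-time reading of 6.5.9 and disregard of section 12.

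The reply does not remove the conflict. The notification clocks start at awareness, and 12.3.2 itself foresees serious events of which the investigator was not aware. After discharge, the scheduled question is a main way to learn of them. Verification of completed eCRFs against source may miss an event treated elsewhere. The 24-hour limit on SADE appears in SAP Table 1 but not in Protocol 3.2 or the SAP 10.9 formula, so it does not fully close the matter.

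**Conclusion.** The visit look-backs in 6.5.6 to 6.5.9 contradict 12.3.1 and SAP 14.1. The first interval is certain on the text: 48 h nominal, 36 to 56 h across the examination window, for every treated patient. The second is conditional: 168 h minus the time of the discharge visit if 6.5.9 means clock time, zero if it means the visit.

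These figures are hours without a visit prompt. The documents give no event rate or discharge times, so no number of missed events or shift in a reported rate can be derived. The realistic exposure is mainly non-serious adverse events, reportable events without sequelae, and serious events the site hears of only by asking. It arises where a site follows the visit text rather than section 12. The eCRF prompts are not in the documents, so whether they repeat the gap is unknown. Severity is minor to moderate, and the primary efficacy analysis is untouched.

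**What to change.** Reconcile the passages so that each look-back begins where the last one ended:

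- 6.5.8: record adverse events since the 24-hour examination, up to the 168-hour or discharge examination, whichever is performed.
- 6.5.9: record adverse events since the previous examination, up to the 90-day examination. This also removes the ambiguity about the 168-hour point.
- Check whether the eCRF visit prompts carry the same wording, and align them if they do.
- For patients already treated, have monitors query the interval from the 24-hour examination to 72 h and, where discharge came early, from discharge to 168 h.

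The cost is two sentences in the protocol, a check of the eCRF and some monitoring queries, with no added visit or test. A few more adverse events may be recorded, so reported rates could be slightly less favourable.

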5.2 Informed consent

Prior to admission to the study, a patient informed consent document will be given to each prospective subject or their Legally Authorized Representative (as defined by the local IRB or ethics committee), including an explanation of the study, duration, explanation of medical record access and patient anonymity, and how their coded data may be transferred, used for publications or in submissions for reimbursement support. The informed consent form will contain language that is non-technical and understandable to the patient or his/her legal representative.

The treatment occurs in an acute emergency situation, so locally required informed consent procedures may apply and will be complied with.

Each potential subject will be provided with written and verbal information regarding the nature of the study in an understandable manner. Adequate time will be allowed for the subject to consider participation in the clinical trial. Signed, written consent will be obtained from each subject prior to data collection and entry into the study. Any coercion or undue influence of potential subjects to participate must be avoided, and the subject's legal rights should not be waived. The investigator or an appropriately designated member of the study staff shall co-sign the consent form, indicating they believe the subject has understood the nature and risks of the study and, in their estimation, the subject clearly understands the scope of the consent. The investigator must inform subjects that they are in a controlled clinical trial, apprise them of their rights as set forth in the informed consent document, and make written documentation that such a discussion took place.

If the subject is not able to sign the informed consent, but has given his/her oral consent to participate, a third party can sign the informed consent for the subject. The procedure will be documented in the medical record. If the subject is not able to give his/her informed consent to participate in the study, a legally authorized relative or independent physician can sign the informed consent for the subject if this is approved by the local Institutional Review Board (IRB) or Ethics Committee (EC).

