6.5.1.1.5 Procedural angiography

Angiography obtained during the procedure will consist of a baseline angiogram, post-device use angiograms (if applicable), a post-final EmboTrap device use angiogram, and if rescue therapy is used, a final post-procedure angiogram.

Baseline angiogram will be obtained prior to device deployment to assess inclusion exclusion criteria as well as to assess clot location. Post-device use angiograms will be obtained immediately after completion of each EmboTrap device and/or rescue therapy pass. The primary endpoint assessment angiogram will be considered any angiogram achieving a rating of mTICI 2b or greater reperfusion, after 3 or less passes of the EmboTrap device, or in the case this is not achieved, the third post EmboTrap device use angiogram. The final post-procedure angiogram will be obtained after all treatments, including any rescue therapies, have been completed. The final post procedure angiogram should comprise a full A-P lateral image.

CT or MRI will also be obtained at 24 hours (16–36 hours) post-procedure to assess any presence

of hemorrhage. It is preferred, but not required, that whether CT or MRI is taken at baseline, to make direct comparison easier, the same imaging modality is obtained at follow-up.

6.5.1.2 *Adverse Events*

Record any adverse events which occur during the procedure.

The procedure description follows.

6.5.2 *Preparation & Delivery*

- Using standard interventional techniques access the arterial system and using angiography, determine the location of the occluded vessel.
- Advance an appropriate Guide Catheter, Sheath or Balloon Guide Catheter as close to the occlusion as possible. Connect a rotating hemostasis valve (RHV) to the proximal end of this catheter and connect to a continuous flush system.
- Select an appropriate Microcatheter. Connect an RHV to the proximal end of the Microcatheter and connect to a continuous flush system.
- With the aid of a suitable guidewire, and using standard catheterization techniques and fluoroscopic guidance, advance the Microcatheter up to and across the occlusion so that the distal end of the Microcatheter is positioned distal of the occlusion.
- Remove the guidewire from the Microcatheter and, if desired, gently infuse contrast media through the Microcatheter to visualize the distal end of the occlusion.

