AJNR March 2008 29: 582-587. “Revascularization Results in the Interventional Management of Stroke II Trial”. Tomsick et al.

19b. mTICI inclusive of the 2c rating:

Consensus clarification*	
0	No perfusion
1	Antegrade reperfusion past the initial occlusion, but limited distal branch filling with little or slow distal reperfusion
2	
Incomplete antegrade reperfusion wherein the contrast passes the occlusion and opacifies the distal arterial bed but there are residual antegrade perfusion deficits
 
 • 2a Antegrade reperfusion of less than half of the occluded target artery previously ischemic territory (eg, in 1 major division of the MCA and its territory) • 2b Antegrade reperfusion of more than half of the previously occluded target artery ischemic territory (eg, in 2 major divisions of the MCA and their territories) • 2c Antegrade reperfusion of >90% but less than TICI 3 or near complete reperfusion
3	Complete antegrade reperfusion of the previously occluded target artery ischemic territory, with absence of visualized occlusion in all distal branches

*Clarification on practical application of this scale based on “Recommendations on Angiographic Revascularization Grading Standards for Acute Ischemic Stroke: A Consensus Statement” of the Stroke J American Heart Association 2013; 44:2650-2663. Originally published online August 6, 2013 Zaidat et al.

20. Monitoring

Act of overseeing the progress of a clinical investigation and to ensure that it is conducted, recorded, and reported in accordance with the CIP, written procedures, this International Standard, and the applicable regulatory requirements.

21. Point of enrolment

Time at which, following recruitment, a subject signs and dates the informed consent form

22. Principal investigator

Qualified person responsible for conducting the clinical investigation at an investigation site.

NOTE 1 If a clinical investigation is conducted by a team of individuals at an investigation site, the principal investigator is responsible for leading the team.

NOTE 2 Whether this is the responsibility of an individual or an institution can depend on national regulations.

23. Recruitment

Active efforts to identify subjects who may be suitable for enrolment into the clinical investigation.

24. Serious adverse device effect (SADE)

Adverse device effect that has resulted in any of the consequences characteristic of a serious adverse event.

25. Serious adverse event (SAE)

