6.2 General Study Population

All consecutive patients presenting for acute ischemic stroke treatment and eligible for the study will be enrolled unless otherwise set out by the clinical site in advance of patient assessment. This could be the case where the site is unable to complete the informed consent process, or where the clinical centre is enrolling stroke patients in multiple studies and has set up a systematic method to enrol presenting patients across studies. Eligibility will be based on the inclusion and exclusion criteria.

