14.1 Adverse Events

Any adverse events which occur during or after the procedure (up to the 90 day follow-up) will be recorded in the database and documented in the Clinical Study Report (CSR). Adverse events will be adjudicated as to the relationship to the EmboTrap device, procedure or the disease state as well to the severity of the event. Subgroup analyses of the points described in the synopsis will be completed.

An AE that occurs after the ICF has been signed and before the treatment with the EmboTrap has started is identified as a pretreatment AE (PTAE). An AE that occurs after treatment using EmboTrap has started will be considered a treatment emergent AE (TEAE).

All AEs will be categorized using the Medical Dictionary for Regulatory Activities (MedDRA) Coding of Adverse Events nomenclature. Standardized nomenclature that will be ascertained includes lowest level and preferred MedDRA terms, MedDRA System Organ Class. Adverse Events will be summarised based on their severity and relationship to the treatment (as defined by the treating site), with the relationship categorised as 1) Definite, 2) Probable/Possible and 3) Unlikely. Unrelated adverse events will not be reported. Separate tables will be used to show 1) all adverse events and 2) serious adverse events.

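### Where consent follows the emergency procedure, starting AE recording at ICF signature contradicts other sections, and no rule counts treated patients for whom nobody ever signs

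*Protocol*

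**What the plan says.** **Consent after the emergency.** Table 1 footnote 2 of the protocol, repeated under SAP Table 2, requires a negative pregnancy test before device insertion "except in the case of local regulations and ethic committee approvals requiring consent post the emergency situation". Section 5.2 adds that locally required emergency consent procedures may apply.

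**Consent first.** Table 1 puts consent at screening, and inclusion criterion 1 requires a signed form. Section 5.2 states: "Signed, written consent will be obtained from each subject prior to data collection and entry into the study". Appendix B item 21 defines the point of enrolment as "Time at which, following recruitment, a subject signs and dates the informed consent form".

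**AE recording from signature.** Footnote 4: "Record all adverse events from the time of signature of the ICF". Section 12.3.1: "The safety assessments will consist of Adverse Events (AE) from the time the ICF is signed through Day 90 for those patients enrolled".

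**AE recording tied to the procedure.** Section 6.5.1.2: "Record any adverse events which occur during the procedure". SAP 14.1: "Any adverse events which occur during or after the procedure (up to the 90 day follow-up) will be recorded in the database". Table 1 marks AE recording in the Procedure column. Section 12.3.1 counts treatment-emergent events from the start of EmboTrap treatment.

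**Patients not entered.** SAP 6.2 allows exceptions to consecutive enrolment that a site has set out before the patient is assessed. Its example is: "This could be the case where the site is unable to complete the informed consent process". Protocol 6.5.1.1 requires a Screening/Enrolment log with the reason for non-participation. It does not ask whether the device was used.

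**The concern.** If consent is sought after the procedure, the angiographic result, an early bleed or an early death can already be known when someone is asked to sign. Two consequences follow.

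First, for a patient who signs later, the rules that start at signature and the rules that cover the procedure give different answers on whether a procedural perforation or early sICH is recorded. sICH and SADEs make up the primary safety endpoint, so its numerator depends on which rule a site follows.

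Second, a treated patient for whom nobody signs is never enrolled, and section 5.2 bars collecting that patient's data. If death or decline makes signature less likely, the patients who remain are a favourable selection. A single-arm study tested against a fixed goal of 0.56 has no control group to share that selection. The SAP 10.3 tipping-point analysis does not reach these patients, because it varies the outcome only for ITT participants with a missing mTICI score. None of the SAP 10.8 sensitivity analyses reaches them either.

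**Working it through.** **1. Passages side by side, for a patient treated first and signed for later**

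| Rule | Is a perforation during the procedure recorded? |
|---|---|
| Table 1 footnote 4 | No, it precedes signature |
| 12.3.1, safety window | No, it precedes signature |
| 6.5.1.2 | Yes |
| Table 1, Procedure column | Yes |
| 12.3.1, TEAE definition | Yes, treatment has started |
| SAP 14.1 | Yes |

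Section 12.3.1 falls on both sides. This is a contradiction between the passages.

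**2. The plan's own figure**

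Inputs (protocol 8.2, SAP 7): n = 176, goal 0.56, assumed rate 0.68, one-sided exact binomial test at 0.025.
- P(X ≥ 111 | 176, 0.56) = 0.0342, above 0.025.
- P(X ≥ 112 | 176, 0.56) = 0.0240, so the cut-off is 112.
- P(X ≥ 112 | 176, 0.68) = 0.906.

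The stated 90% power at 176 is reproduced.

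**3. How many uncounted failures would reverse a pass**

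Keep x successes, add k treated but unsigned patients as failures, and compare x with the cut-off at n = 176 + k.

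| Observed | Last k that passes | First k that fails |
|---|---|---|
| 112/176 | 0 (112/176, p = 0.0240) | 1 (112/177, p = 0.0297) |
| 115/176 | 5 (115/181, p = 0.0239) | 6 (115/182, p = 0.0295) |
| 120/176 (68.2%, the design rate) | 13 (120/189, p = 0.0220) | 14 (120/190, p = 0.0271) |

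At the design rate, reversal needs 14 of 190 treated patients, or 7.4%, all unsigned and all failures.

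**4. Effect on the chance of a false pass**

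Assumptions not in the documents: a share f of treated patients is never signed for, and their success rate is q. If the true rate in all treated patients is exactly 0.56, the rate among 176 signed patients is

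p = (0.56 − f·q) / (1 − f).

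For example, f = 0.02 and q = 0 give 0.56/0.98 = 0.5714. The table shows P(X ≥ 112 | 176, p):

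| f | q = 0 | q = 0.30 | q = 0.56 |
|---|---|---|---|
| 0% | 0.024 | 0.024 | 0.024 |
| 1% | 0.034 | 0.028 | 0.024 |
| 2% | 0.047 | 0.033 | 0.024 |
| 3% | 0.065 | 0.039 | 0.024 |
| 5% | 0.117 | 0.053 | 0.024 |

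The last column is loss unrelated to outcome, which does no harm to the test.

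**5. Safety rate**

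Assume a true event rate of 8% (not a figure from the plan) and that every lost patient had an event. The observed rate is (0.08 − f)/(1 − f), which gives 7.1%, 6.1%, 5.2% and 3.2% at f = 1%, 2%, 3% and 5%.

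**The case against.** The case on the other side has weight on several points.

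- **Analysis sets.** A reader might infer that treated patients without a signature are excluded from every analysis set. The definitions do not say so. SAP 9.1 defines ITT by angiographic eligibility, SAP 9.4 defines the Treated Set by treatment regardless of eligibility, and neither mentions consent. The loss in practice follows from 5.2 and Appendix B item 21, because a patient never signed for has no study data to analyse.
- **Surrogates.** Death or decline does not by itself prevent entry. Under 5.2 a third party may sign after oral consent, and a relative or independent physician may sign where the IRB/EC approves. This reduces the loss, but it depends on local approval and does not help where consent is refused.
- **SAP 6.2.** A reader might take it as permission to drop patients once the result is known. It is not: the exceptions must be set out before the patient is assessed.
- **AE window.** A reader might infer that procedural events are plainly excluded. Four other places call for them, and footnote 4 is attached only to the Screening cell of Table 1. The core laboratory also reads all angiograms and the CT/MRI, and the CEC adjudicates what it documents. The conflict in wording remains, chiefly because 12.3.1 states the same start without that limit.
- **Exposure.** The only direct text on consent after the emergency is an exception to a pregnancy-test rule. The numbers of sites and patients are not given.
- **Direction.** mTICI is fixed on the table, and refusal need not follow it. Loss unrelated to outcome leaves the error rate at 0.024.

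These points limit the concern to a contradiction and a missing count. They do not remove either.

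**Conclusion.** The point holds in limited form. The documents foresee treatment before consent at some sites and give conflicting AE start times for patients who sign afterwards. They also give no rule for counting treated patients who are never signed for. That the loss would depend on outcome is plausible but not shown.

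The size is unknown and may be zero. At the planned success rate the efficacy conclusion is robust, since 120/176 survives 13 added failures. Nearer the cut-off it is fragile: 115/176 survives 5 and 112/176 none. The false-pass figures rest on assumed values of f and q, and their upper end requires every lost patient to be a failure. Without a count, the report could not show whether the loss was nil, harmless or material.

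**What to change.** 1. Amend Table 1 footnote 4 (and the same note under SAP Table 2) and section 12.3.1 so that AE recording starts at the earlier of consent-form signature and arterial puncture. This matches 6.5.1.2 and SAP 14.1. The SAP describes enrolment in the past tense; if recruitment is complete, state the rule in the SAP and confirm that it was applied to patients who signed after the procedure.
2. From the existing Screening/Enrolment log, report beside ITT the anonymous number of angiographically eligible patients treated with EmboTrap without a signed form. Give the reason (death, incapacity, refusal), as local IRB/EC rules allow.
3. If that number is above zero, extend the SAP 10.3 tipping-point analysis to add these patients, from all failures to all successes. This uses only their number, not their individual data.

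The cost is one wording change, one log field and one line of analysis. The downside is a slightly less favourable sensitivity range.
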